## 6.1 Sample Size Considerations

The study is designed to provide descriptive statistics of preliminary safety and immunogenicity assessments only, and thus no formal sample size calculation has been performed. It is planned to randomise 10 subjects into each of the six treatment arms, which is considered an appropriate study size at this phase of development of Vaccine FP-02.2.

## 6.2 Randomisation

Subjects will be randomly assigned to blinded treatment groups by the Interactive Response Technology (IRT) cohorts as described in [Table 2](#). The first 15 subjects, forming cohort 1, will be randomised in a 2:1 ratio to either FP-0.2 low dose or placebo. The 30 subjects in cohort 2 will be randomised in a 2:2:1:1 ratio to FP-0.2 low dose + IC31® adjuvant, FP-0.2 high dose, Placebo or IC31® adjuvant only. Finally, the final 15 subjects in cohort 3 will be randomised in a 2:1 ratio to either FP-0.2 high dose + IC31® adjuvant or IC31® adjuvant only respectively.

Following completion of the Screening activities, subjects who meet the all the inclusion and none of the exclusion criteria will be registered by the IRT.

The first subjects in each treatment arm of a cohort (i.e. active alone, active +IC31®, placebo and IC31® alone, as applicable) will form the sentinel group. Where possible, all sentinel subjects per treatment will be dosed at the same clinical site. Subsequently subjects in each cohort will be randomised to the applicable active or control treatment, to meet the required number of subjects to be dosed in each arm.

**Table 2: Study Cohorts and Treatment Arms**

Cohort	Treatment arm	Planned number of subjects
1	Placebo	5
	FP-0.2 Low dose	10
2	Placebo	5
	IC31® adjuvant only	5
	FP-0.2 Low dose + IC31® adjuvant	10
	FP-0.2 High dose	10
3	IC31® adjuvant only	5
	FP-0.2 High dose + IC31® adjuvant	10

Subjects in Cohort 1 were randomised according to a randomisation list prepared by Hammersmith Medical Research, and subjects in Cohort 2 and 3 will be randomised according to a randomisation list prepared by Parexel, following the transition of the study to PRA.

## 7.0 Study Variables and Covariates

### 7.1 Primary Variables

- Solicited adverse events (AEs) related to injection site tolerability during the week following each vaccine administration.
- Unsolicited AEs through day 85
- Serious adverse events (SAEs) and AEs of special interest (AESIs) through 6 months after last vaccine dose
- Vital signs
- ECGs
- Safety laboratory assessments including laboratory assessment of liver inflammation and function

## 7.2 Secondary Variables

FP-02.2-specific T cell immunity (measured by the number of cells producing interferon gamma (IFN- $\gamma$ ) in response to exposure to 9 individual peptides. Further details are given in [section 12.7.1](#).

# 8.0 Study Time point Definitions

## 8.1 Baseline

Unless specified otherwise, baseline will be defined as the latest assessment taken prior to the first dose of investigational product.

## 8.2 Relative Day

Relative day will be calculated as the date of assessment or event minus the date of IP plus 1 (eg, the day of first dose will be Day 1). For days prior to the first dose of IP (the day prior to first dose will be Day -1), relative day will be calculated as the current date minus the date of first dose of IP.

## 8.3 Study Visit Intervals

As per [Table 1](#), Visit intervals are as follows:

- Screening and randomisation: subjects must be screened -1 to 28 days ( $\pm 2$  days) and can be randomised to treatment up to 3 days prior to the first injection.
- First dose: Visits 1 and 2 must be done on Days 1 and 2, respectively; Visit 3 may be done within  $\pm 1$  day of Day 8.
- Second dose: Visit 4 may be done 28 days ( $\pm 7$  days) after Visit 1; subjects must be contacted the day after Visit 4; Visits 5 should be done 7 ( $\pm 1$  day) days after Visit 4.
- Third dose: Visit 6 may be done 28 days ( $\pm 7$  days) after Visit 4; subjects must be contacted the day after Visit 6; Visits 7 and 8 may be done 7 ( $\pm 1$  day) and 28 ( $\pm 1$  day) days after Visit 6.
- Follow-up: Visit 9 must be done at 24 ( $\pm 28$  days) weeks after the last dose (Visit 6).

The scheduled assessments may shift in instances where a visit window is used; subsequent visit dates should be recalculated from the date of the new visit. If a second dose visit is missed, the dose can be given 6 weeks after the first dose and noted as out of window. If the dose is later than 6 weeks, the second dose visit can be skipped and given at Visit 3 at 8 weeks as per schedule to avoid a delay in the schedule. Subjects receiving fewer than 3 doses during the study will be excluded from the Immunogenicity Analysis Set defined below in [Section 9.4](#).

Data will be summarised according to the scheduled visit that the data was recorded under in the eCRF. Data from unscheduled or repeated visits will not be included in the summary tables except in derivation of baseline values, but will be listed. If an assessment is repeated due to a damaged sample leading to unusable data in the original instance, the correct sample as identified by medical review will be mapped to the scheduled visit.

Where this SAP refers to summaries 'by visit' or 'by assessment time point' etc., this is taken to be visits and assessments as per protocol version 6. Under previous versions of the protocol, additional visits were in place, giving a different structure.

For subjects that consented to earlier protocol versions and attended additional visits to version 6 as per the protocol they consented to, the results from these assessments will not contribute to summaries by visit. These data will be included in individual subject listings only.

## 8.4 Study Visit Labelling

Visits will be labelled in table summaries (according to the schedule outlined in [Table 1](#)) as follows:

- “Screening”
- “Baseline”
- “Visit X, Day X (Pre/Post-Dose X)” for all scheduled visits, apart from screening and baseline.
- “Day X (TC)” For post-treatment calls relating to injection site tolerability.
- “Last visit” Defined as a subject’s last visit in the study prior to termination or completion.

Listings will use the same visit labels and will also include “Unscheduled” as applicable.

Note that in the summary tables ‘Baseline’ will be the value derived as described in [Section 8.1](#), which will usually be the Visit 1, Day 1 assessment, but may also be a screening or unscheduled assessment.

## 9.0 Analysis Sets

Membership of analysis sets will be determined at a blinded data review meeting convened by Altimmune conducted between database freeze and database lock.

### 9.1 Randomised Set

The Randomised Set consists of all subjects for whom a randomisation number has been assigned.

### 9.2 Safety Analysis Set

The Safety Analysis Set will contain all subjects who were randomised and received at least 1 injection of Vaccine FP-02.2, Vaccine FP-02.2/IC31®, placebo or IC31®. The Safety Analysis Set will be used for all safety analyses and will be analysed according to the treatment received.

### 9.3 Full Analysis Set

The Full Analysis Set comprises all members of the Safety Analysis Set with at least one complete post-vaccination immunogenicity result.

### 9.4 Immunogenicity Analysis Set

The Immunogenicity Analysis Set comprises all members of the Full Analysis Set with immunogenicity assessments at screening followed by days 1, 8, 29, 36, 57, 64 and 85, a full set of 3 doses of investigational product and with no important protocol deviations adjudicated as relevant by the medical team. Subjects with missing day 1 peripheral blood mononuclear cells (PBMC) may be included if screening PBMC data are available to calculate a baseline. [Section 12.2](#) gives more information about the classification of important protocol deviations.

## 10.0 Interim Analyses

### 10.1 Safety Review Committee meetings

#### 10.1.1 Continued Recruitment to a Cohort

After the assessments on Day 8, the SRC will meet and review the safety data from the sentinel group and recommend whether or not the remaining subjects of a cohort should be dosed. Any principal investigator with subjects in the sentinel group will provide input to the SRC meeting. The SRC will use listings from the clinical database at the appropriate time point for cohort recruitment decisions rather than outputs programmed using SAS.

### 10.1.2 Dose Escalation

In order to progress to the next cohort, the SRC with input from the Investigators contributing subjects will meet to review safety data up to Day 36 from Cohort 1. Following this review subjects may be dosed in Cohort 2 assuming the SRC has identified no safety concerns. Similarly, subjects may be dosed in Cohort 3 after review of safety data up to and including Day 36 from subjects in Cohort 2.

If safety and tolerability data are not acceptable the SRC may recommend lowering the dose of FP-02.2 or omitting the use of IC31®.

All data used to support dose escalation will be quality checked as per the data management plan. Dose decisions between cohorts will be documented. The SRC will use listings from the clinical database at the appropriate time point for dose escalation decisions rather than outputs programmed using SAS.

### 10.2 Primary and Follow-up Analyses

After all participants in cohort 3 have completed Day 85, the primary analysis of the safety data collected up to Day 85, immunogenicity (except HLA genotyping) and virology data will be performed. A secondary follow-up analysis of all immunology and safety data, including those collected between Day 86 and Day 225 for all cohorts will be conducted. The Investigators, all site staff, the subjects and trial monitors will remain blinded between the two analyses. Staff at PRA and Altimmune will unblind at the primary analysis at Day 85 of the final participant in cohort 3.

For the primary analysis, the data will be cut at day 85 for each individual subject regardless of their current progress in the study. Adverse events and concomitant medications occurring after day 85 will not be included in the outputs for the primary analysis.

The information from the primary analysis is required to inform the design of the next clinical study and confirm the formulation and dose to use.

This SAP describes the analyses that will be done at both of these time points. The same tables, figures and listings listed in [Appendix 1](#) will be produced at both time points.

## 11.0 Data Review

### 11.1 Data Handling and Transfer

Data handling and transfer will be discussed in greater detail in the PRA Data Management Plan.

### 11.2 Data Screening

Beyond the data screening built into the PRA Data Management Plan, the PRA programming of analysis datasets, tables, figures, and listings (TFL) provides additional data screening. Data issues identified during programming in preparation for dry runs will be raised to Data Management. The post-freeze TFL run on the frozen database will be discussed with Altimmune in a data review meeting to identify any final data issues and seek corrections prior to database lock. The PRA statistician and Altimmune must approve database lock.

### 11.3 Blinded Data Review Meeting

A Blinded Data Review meeting will be convened by Altimmune after the database has been frozen but prior to database lock and before the study is unblinded.

The terms of reference of the Blinded Data Review Meeting shall include but not be limited to:

- the determination of whether important protocol deviations are relevant to the interpretation of the immunogenicity and virology data
- the allocation of subjects to analysis sets

- a review of missing data and of outliers
- a review of the distribution of the efficacy variables, considering any implications for the proposed method of statistical analysis
- the finalisation of the SAP

The Blinded Data Review Report will include the final categorisations of important and non-important protocol deviations, lists of the members of the various analysis sets and the rationale for any changes to the SAP.

The Blinded Data Review Report will be finalised before the blind will be broken. Formal records shall be kept of when the SAP was finalised as well as when the blind was subsequently broken.

## 12.0 Statistical Methods

Statistical analyses will be performed using Version 9.4 (or newer) of SAS® on a suitably qualified environment.

Unless otherwise noted, categorical variables will be summarised using counts and percentages. Percentages will be rounded to one decimal place, except 100% which will be displayed without any decimal places. Percentages will not be displayed for zero counts.

Continuous variables will be summarised using the number of observations (n), mean, standard deviation (SD), median, quartiles, minimum and maximum. The minimum and maximum values will be displayed to the same level of precision as the raw data, the median, quartiles and mean to a further decimal place and the SD to two additional decimal places. The maximum presentation of decimal places will be to 4 decimal places.

No formal hypothesis testing will be performed for this study. All endpoints are considered as exploratory and will be summarised descriptively. However, standard errors and 95% confidence intervals (CIs) will be displayed for change from baseline for specified immunogenicity and virology endpoints.

No pooling of centres, stratification or analysis by subgroups will be performed during this study.

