The design of FP-02.2 takes advantage of a vaccine platform developed by Altimmune (formerly Vaxin, formerly Immune Targeting Systems) that is dedicated to the development of synthetic peptide-based vaccines aimed at promoting T cell responses against mutating viruses. This platform comprises two complementary arms i) a bioinformatics methodology to select broadly immunogenic long peptide sequences against viral regions conserved across genotypes and ii) a novel vaccine formulation using multiple fluorocarbon-linked peptides to produce a depot following IM administration that prolongs vaccine half-life and enhances immunogenicity in situ.

The nine peptides included in FP-02.2 have been selected based on an extensive screening process relying on bioinformatics, preclinical screening and key manufacturing aspects. FP-02.2 has been designed to deliver the most conserved domains of HBV surface, core and polymerase antigens (corresponding cumulatively to 18.7% of the HBV proteome) to achieve multi-epitopic CD4+ and CD8+ T cell responses, irrespective of ethnicity, human leukocyte antigen (HLA) background or infecting HBV genotype. This approach is required to optimise antiviral activity by exerting broad immune pressure on the virus and consequently minimising viral escape mechanisms. This approach has a significant advantage over other vaccine approaches in development, such as DNA or viral vaccines, by allowing for multi-use booster capability.

In two study arms, FP-02.2 will be used in conjunction with the vaccine adjuvant IC31® to potentially increase immune responses to the vaccine and overcome immune tolerance and the suppression mechanism observed in CHB. A fixed dose of IC31® will be used (500nmol KLK/ 20nmol ODN1a) that has been previously tested in 8 Phase I/IIa clinical trials in combination with TB or seasonal influenza vaccines.

This study will be the first in man study for Vaccine FP-02.2 and will assess the safety and tolerability of three IM injections of a therapeutic hepatitis B fluoropeptide vaccine in HBeAg-negative hepatitis B patients as an add-on treatment to entecavir or tenofovir. Immunogenicity analysis of the specific T cell responses induced by Vaccine FP-02.2 or Vaccine FP-02.2/IC31® will be undertaken to aid selection of the optimal dose to be used for future studies.

Clinical evaluation of Vaccine FP-02.2 will seek to address these key issues:

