1. At estimated effective dose(s), and in the presence or absence of an estimated effective dose of a compatible adjuvant, is the vaccine safe and tolerated in nucleoside analogue (NA)-treated HBV patients with stable disease?
2. Is there evidence of induction of an immune response to the vaccine and what impact does an adjuvant (IC31®) have on the immune response – i.e. magnitude and anti-viral phenotype of T cell response.
3. To what extent is the immune response robust and durable?
4. Is there evidence of a pharmaco-dynamic effect of the vaccine indicative of potential efficacy i.e. reduction in serum HBsAg and/or increase in serum antibody to HBsAg; if so is the response dose dependent and is the response modified by inclusion of IC31®?

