4 TRIAL DESIGN

This is a double-blind, randomised, placebo-controlled, dose-ascending study to evaluate the safety, tolerability and immunogenicity of Vaccine FP-02.2 in HBeAg-negative hepatitis B patients as an add-on treatment to entecavir or tenofovir.

Actively treated subjects will receive either a Low or High dose of Vaccine FP-02.2 with or without IC31®.

A placebo arm is included in the study. Safety and immunogenicity data generated from the placebo arm will allow comparison to data generated from the Vaccine FP-02.2 High and Low dose study arms. The placebo group is also necessary to understand the rate of natural HBsAg seroconversion in an untreated study arm. An IC31® alone arm is included in the study which will additionally allow comparison of safety and immunogenicity data with data generated from the Vaccine FP-02.2 High and Low dose/IC31® study arms.

Approximately of 60 subjects (excluding replacements for subjects deemed ineligible after dosing) will complete this trial and will be assigned equally to 6 study arms (approximately 10/study arm).

Screening will occur up to 28 days prior to the first injection.

Up to 3 days before the first injection, eligible subjects will be randomised to treatment arm as shown in Table 2, depending on the cohort.

Subjects will receive 3 injections at intervals of 28 days (Day 1, Day 29, and Day 57). On the days of the injections the subjects will stay in the clinic for at least 4 hours after the first injection and 2 hours after the second and third injections and be monitored closely including an assessment of local reactions at the injection site. Approximately 24 hours after the first injection, the subjects will be asked to attend the clinic for safety assessments. For subsequent injections, subjects will receive a telephone call approximately 24 hours after each injection for safety follow-up. The subjects will be asked to return to the clinic 7 days after each injection for further assessments as well as 28 days after the last injection (Day 85). A follow-up visit will be performed 6 months after the end of the treatment period (i.e. 6 months after the last dose).

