#### 12.7.1.1 Immune Response

Descriptive statistics (mean, SD, median, quartiles, minimum and maximum) will be generated by treatment group and time point for the following ELISpot score variables:

- ELISpot scores and change from Baseline for individual peptides and LPMIX9
- Sum ELISpot scores and change from baseline across the 9 individual long peptides

Sum ELISpot score is defined as the sum of the 9 ELISPOT scores from the 9 individual peptides.

In addition, standard errors and 95% CIs derived from a one-sample t-test will be presented for change from baseline.

Baseline is defined as the mean of the ELISpot scores prior to the first injection.

In addition, line plots of the mean ( $\pm$  SE) ELISPOT scores over time will be presented by treatment group for each individual peptide, LPMIX9 and the sum score of the 9 individual peptides for the cultured assay over the Immunogenicity Analysis Set. If the Full Analysis differs from the Immunogenicity Analysis Set, then the figures will be repeated for the Full Analysis Set.

Similarly, line plots of each individual patient's ELISPOT score over time will be presented, grouped by treatment group for each individual peptide, LPMIX9 and the sum score of the 9 individual peptides for the cultured assay over the Immunogenicity Analysis Set. If the Full Analysis differs from the Immunogenicity Analysis Set then the figures will be repeated for the Full Analysis Set.

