## 12.8 Virology Analysis

Blood samples will be collected for the assessment of virological parameters at the times indicated in **Table 1**.

Descriptive statistics for Virology parameters values:

- Quantitative Hepatitis B surface antigen (HBsAg) [presented in log10]
- Hepatitis B virus (HBV) DNA

and changes from baseline (in SI units) at each assessment time point will be presented by treatment group and visit for all subjects in the Immunogenicity Analysis Set and repeated for the Full Analysis Set if different.

Standard errors and 95% CIs derived from a one-sample t-test will be presented for change from baseline for HBsAg.

In addition, a line plot of the change from baseline in log10 HBsAg at each timepoint will be presented by treatment group.

The antibody to hepatitis B surface antigen (HBsAb) will be summarised by 'seroconverted' or 'not seroconverted' by visit for the Immunogenicity Analysis Set and repeated over the Full Analysis set if different. Seroconversion corresponds to HBsAb > 10 mIU/mL.

Individual subject results for all virology parameters will be listed for the Full Analysis Set.

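### Only within-arm intervals are planned for ELISpot and HBsAg; a short list of baseline-adjusted between-arm differences should be fixed before the Day 85 unblinding

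*SAP*

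**What the plan says.** SAP 12.0 rules out formal hypothesis testing and calls every endpoint exploratory, with one addition: "standard errors and 95% confidence intervals (CIs) will be displayed for change from baseline for specified immunogenicity and virology endpoints". Section 12.7.1.1 makes this concrete for ELISpot ("standard errors and 95% CIs derived from a one-sample t-test will be presented for change from baseline") and section 12.8 for HBsAg ("Standard errors and 95% CIs derived from a one-sample t-test will be presented for change from baseline for HBsAg"). These are summaries by treatment group, so each interval describes one arm. Appendix 1 lists no table or figure of a treatment difference, and no model. Baseline is used only to form the change, never as a covariate.

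The documents also say what the data are for. Protocol section 4 says the placebo data "will allow comparison to data generated from the Vaccine FP-02.2 High and Low dose study arms", and gives the IC31-only arm the same role for the adjuvanted arms. Protocol section 2 says the immunogenicity analysis "will be undertaken to aid selection of the optimal dose to be used for future studies". One of its key issues, which are not listed objectives, asks "is the response dose dependent and is the response modified by inclusion of" IC31. SAP 10.2 calls the Day 85 analysis "required to inform the design of the next clinical study and confirm the formulation and dose to use", and adds: "Staff at PRA and Altimmune will unblind at the primary analysis at Day 85 of the final participant in cohort 3".

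**The concern.** The decision resting on Day 85 is a choice between arms, and each planned interval is about one arm. A vaccine-arm interval above zero does not say whether the control arm moved as well. A reader can work out a crude difference and its standard error from the by-arm n, mean and SD. A baseline-adjusted difference cannot be recovered from those tables. No list says which differences matter, so the choice could be made after the people who will make it have seen the results by arm. SAP 12.7.2 requires only that exploratory analyses in the study report be labelled exploratory. It names optional summaries by cohort, country or gender, but no between-arm contrast.

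**Working it through.** **Plan's own figure.** SAP Table 2: 5 + 10 + 5 + 5 + 10 + 10 + 5 + 10 = 60, i.e. 10 in each of six arms with controls pooled over cohorts. This matches the stated total of about 60. No SD, effect size or precision target is given.

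**Assumptions.** Equal SDs, normal data and full n. Widths are in SDs of change from baseline unless stated.

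**Unadjusted 95% half-widths**
- Planned within-arm interval, n = 10: t(9)/√10 = 2.262/3.162 = 0.72.
- Difference of two arms, SD from all six arms (54 df): 2.005 × √(2/10) = 0.90.
- Difference of two arms, SD from those two only (18 df): 2.101 × √(2/10) = 0.94.
- Within-cohort active v control, 10 v 5: √(1/10 + 1/5) = 0.548. Times t(52) = 2.007 this is 1.10; with the two cells only (13 df) it is 1.18.
- If 8 per arm were kept (assumption): 0.84 within an arm, and 1.07 for a difference (14 df).

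The unadjusted difference is therefore 25% (0.897/0.715) to 31% (0.940/0.715) wider than the planned interval.

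**Baseline-adjusted difference.** Let ρ be the baseline-to-Day 85 correlation, with one baseline measurement of the same variance. In SDs of a single measurement:
- planned within-arm half-width = 0.715 × √(2(1 − ρ));
- six-arm ANCOVA half-width (53 df) = 2.006 × √0.2 × √(1 − ρ²) = 0.897 × √(1 − ρ²);
- ratio = (0.897/0.715) × √((1 + ρ)/2) = 1.254 × √((1 + ρ)/2).

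| ρ (assumed) | Six-arm ANCOVA ratio (53 df) | Two-arm ANCOVA ratio (17 df) |
|---|---|---|
| 0 | 0.89 | 0.93 |
| 0.5 | 1.09 | 1.14 |
| 0.7 | 1.16 | 1.22 |
| 0.9 | 1.22 | 1.29 |

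The six-arm ratio passes 1 at ρ of about 0.27. Small losses from chance baseline imbalance are ignored.

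**Why two within-arm intervals do not replace a difference.** Suppose two arms of 10 share the same true change, and p is the chance that an arm's lower limit exceeds zero. The pattern of vaccine interval above zero and control interval not has chance p(1 − p). With no change this is 0.025 × 0.975 = 2.4%. At an assumed shared change of 0.7 SD, p = 0.506 and the chance is 25%. The SAP states no such reading rule, so this is illustration only.

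**Which contrasts are concurrent (SAP 6.2, Table 2).** Each active arm has a control randomised in its own cohort, 10 v 5. Cohort 2 also randomises Low+IC31 with High, 10 v 10, and IC31-only with Placebo, 5 v 5. High v Low, High+IC31 v Low+IC31, Low+IC31 v Low and High+IC31 v High all cross cohorts.

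**Chance exclusions of zero from the proposed display.** Simulated null trials, unadjusted, per endpoint, at least one interval excluding zero: about 20% for the 5 main contrasts and 28% for all 9. With the 4 within-cohort differences added it is about 34% (SD from the six-arm model) to 35% (SD from the eight cohort-by-arm cells).

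**The case against.** The strongest reply is that nothing is broken. The sample is one of convenience, all endpoints are exploratory, no efficacy analysis is planned (SAP 12.5), and the secondary objective is to measure response. No passage promises a between-arm estimate. By-arm summaries and plots do allow comparison in the ordinary sense, SAP 12.7.2 requires labelling, and SAP 11.3 finalises the SAP before the blind is broken. All of that stands, and it is why this is an improvement rather than an error. It does not remove the gap: an estimate with an interval is not a test, and the SAP already shows intervals under its no-testing rule.

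A reader might infer more than the documents support:
- *The within-arm interval always understates the uncertainty.* It is narrower than the unadjusted difference. Against the adjusted one it depends on a correlation that the documents do not give.
- *Every dose or adjuvant comparison crosses cohorts.* Cohort 2 contains two that do not.
- *Cohort 1 is not comparable with the rest.* It had a different randomisation list (SAP 6.2), and its data up to the transition sat in another database under earlier protocol versions (SAP 13.1). Nothing shows that this moved ELISpot or HBsAg. It only makes control results by cohort worth seeing.

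It is also fair to say that the intervals will be wide.

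**Conclusion.** The point holds as an inexpensive improvement that should be made. The plan shows uncertainty for change within each arm but not for the differences on which a formulation and dose choice rests, and it fixes no contrasts before sponsor and CRO staff unblind. The unadjusted difference has a half-width of 0.90 to 0.94 SD of change, against the 0.72 that will be shown. For the adjusted difference the six-arm ratio is 0.89 to 1.22 over assumed correlations of 0 to 0.9. These figures rest on equal SDs, roughly normal data and 10 evaluable subjects per arm. Thresholded ELISpot scores may not be normal, and the Immunogenicity Analysis Set may be smaller. The reading that the plan contradicts itself is not supported.

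**What to change.** Keep the no-testing rule. In SAP 12.7.1.1 and 12.8 add a descriptive ANCOVA at Day 85 for cultured Sum ELISpot and log10 HBsAg, both already in top-line tables. Use treatment arm as factor and the SAP-defined baseline as covariate, and show differences with 95% CIs.

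- **Main set:** Low − Placebo; High − Placebo; Low+IC31 − IC31; High+IC31 − IC31; and Low+IC31 − High, with a note that it is concurrent in Cohort 2 but changes dose and adjuvant together.
- **Supportive set,** labelled as crossing cohorts and not concurrently randomised: High − Low; High+IC31 − Low+IC31; Low+IC31 − Low; High+IC31 − High.
- **By-cohort display:** control arms by cohort beside the pooled column, with the four within-cohort 10 v 5 differences as sensitivity. Reword the last sentence of SAP 12.0 to permit this.
- **Cultured score:** before lock, state what score a cultured response takes when it is not reported, and whether scores can be negative. Appendix 2, step 8, sets sub-threshold scores to zero only for the ex vivo assay. Read literally, a cultured response of 50 with background mean 100 and SD 10 passes the threshold (50 > 3 × 10) and scores 50 − 100 = −50. Then fix the analysis scale at the blinded data review.
- **Multiplicity:** state that none is controlled, and print the chance-exclusion rate for the intervals actually shown (about 20%, 28%, or 34 to 35% per endpoint, as in the working, with its assumptions).

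Cost: wording in SAP 2, which SAP 4.0 places after the blinded review and before lock, and two extra tables, or four if repeated because the analysis sets differ. Protocol 10.3 requires no protocol amendment, only that the change be described in the SAP and study report. The downside is wide intervals that will not settle dose or formulation alone, and some exclusions of zero by chance.
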